### **Radiographic diagnosis of palatal impaction:**

The horizontal parallax method will be used since it is more reliable than vertical parallax. A periapical film would be placed in mouth on the palatal aspect of the area where the tooth is normally situated. The X-ray tube is directed at right angles to a tangent to the line of the arch at this point and at appropriate angle to the horizontal plane as for any periapical view. A second film is placed in the mouth in the identical position but, on this occasion, the x-ray tube would be shifted distally but held at the same angle to the horizontal plane and directed mesially. To do this the tube should describe 30-45° of an arc of a circle, whose center is somewhere in the middle of the palate. The IOPA Xray which would be taken from distal will be marked "D" for identification.

### **Randomization:**

Randomization procedures and reporting include the following steps.

1. Generation of the random allocation sequence, including details of any restrictions:  
 Minimization, a form of restricted randomization, is considered to be a dynamic method, since the randomization list is not produced before the trial starts, but during participant recruitment. Additionally, minimization, in contrast to the previous methods, is considered to be an adaptive randomization technique, since future participant allocation depends on previous assignments. Once consent had been obtained, each participant will be randomly allocated to group 1 or group 2.

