#### **2. Allocation concealment and implementation of the random allocation sequence:**

Blinding of the investigator is not possible so to reduce bias one of the staff assistant who was neutral towards treatment will be allocated the job of assigning patient in the two treatment groups. The first 5 patients will be allocated according to simple randomization and from 6th patient onwards minimization will be followed.

The prognostic factors or predictors will be used like severity of impaction, age, oral hygiene, presence of crowding, and rotation of canine. The severity of the canine impaction will be assessed by a single blinded assessor, from the pretreatment panoramic imaging film, using the criteria described by Ericson and Kurol.

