### **Treatment Protocol:**

The orthodontic treatment will be done by single orthodontist who will follow a strict protocol as follows:

1. Initial orthodontic alignment will be aimed at creating space in the maxillary arch with fixed appliance therapy (0.022 slot) .The surgical procedure will be done after reaching a full size wire of 19X25 S.S with open coil spring to maintain space for the permanent canine. Anchorage preparation will also be done with the help of TPA.

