#### Open Surgical Exposure of Impacted canine:

- Surgically uncover the canine tooth and bone removal exposing the largest diameter of the ectopic canine crown. The edges need to be substantially trimmed back and dental follicle removed to prevent regrowth of the very thick palatal mucosa. For a deeply buried and palatally displaced tooth, the exposure will additionally need to be maintained using surgical pack.
- Coe-pack surgical dressing (GC America Inc, Alsip, IL) will be left in place.
- The patient will be reviewed 10 days later, the surgical pack will be removed and the bracket will be bonded and loading will be done by traction forces. Once the tooth has

erupted sufficiently for an orthodontic attachment to be positioned at its correct location to bring the tooth into line.

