#### **8. MY SPECIFIC FUNCTION & ROLE IN THE PROPOSED STUDY:**

After allocation of patients in both the groups, being an investigator, my role shall be clinical intervention from bonding the brackets to orthodontic dis-impaction of impacted canines to its normal position. Being a clinical research project, it will be

help in practicing both clinical, and research analysis. It will be a team effort i hope to contribute to the practice of evidence based dentistry through this project. By performing it to best of my abilities and minimizing bias.

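### Allocation at consent comes before an alignment phase that both arms share; allocating when surgery is booked would be a cheap improvement of optional to moderate priority

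*Protocol*

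**What the plan says.** Timing. Step 1 of the Randomization section ties allocation to consent: "Once consent had been obtained, each participant will be randomly allocated to group 1 or group 2". No later trigger is named. Section 8 gives the same order from the investigator's side: "After allocation of patients in both the groups, being an investigator, my role shall be clinical intervention from bonding the brackets to orthodontic dis-impaction". Treatment Protocol, step 1, then describes one initial alignment phase for all patients, and surgery waits for its end: "The surgical procedure will be done after reaching a full size wire of 19X25 S.S with open coil spring". The first instruction that differs by arm is the exposure itself; for the open arm it begins "Surgically uncover the canine tooth and bone removal exposing the largest diameter of the ectopic canine crown", and the closed arm has its own section with a raised flap.

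Method. Under minimisation "future participant allocation depends on previous assignments", and step 2 adds: "The first 5 patients will be allocated according to simple randomization and from 6th patient onwards minimization will be followed". Five factors are listed: severity, age, oral hygiene, crowding and canine rotation. The protocol does not say whether the favoured arm is always taken or only with some probability.

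Blinding. Step 2 states "Blinding of the investigator is not possible so to reduce bias one of the staff assistant who was neutral towards treatment", and gives that assistant the task of assigning patients. The only blinded reading mentioned is before treatment: "The severity of the canine impaction will be assessed by a single blinded assessor".

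Outcome. The periodontal readings that belong to the second primary outcome are entered on Annexure 2, one month after debond. The first field of that form is the group.

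**The concern.** Nothing that differs between the arms happens between consent and surgery, so the arm is not needed during alignment. Allocating at the start of that phase has three consequences.

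- A patient who leaves during alignment belongs to the randomised set but can tell us nothing about open against closed exposure.
- That patient still counts in the running totals, so minimisation balances those who consented rather than those who are operated on.
- The orthodontist, who is not blinded, can know the arm throughout a phase where it should make no difference.

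At stake are a randomised set eroded before the techniques diverge and some of the balance that minimisation was chosen to secure in a trial of 40.

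A separate point, to be judged on its own, is that the protocol plans no masking of the manual periodontal readings and does not say who takes them.

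**Working it through.** **Inputs from the protocol.** Total of 40, 20 per arm (Estimation of Sample Size); simple randomisation for the first five patients, then minimisation on five factors (Randomization, step 2). The protocol gives no figure on allocation timing, so there is none to reproduce. The total of 40 is used as stated. Its own two-sided inputs (0.5 mm, SD 0.61 mm, 80% power) give 2 × (0.61 × (1.960 + 0.842) / 0.5)² = 23.4, so 24 per arm or 48. That is a different matter, which the timing of allocation neither causes nor cures.

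**Assumptions.** Pre-surgical loss L of 5%, 10% or 15%, at random; the documents give neither a loss rate nor the length of alignment.

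**1. Numbers operated on.** Lost of 40: 2, 4, 6. Operated: 38, 36, 34, under either timing.

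**2. Chance imbalance if exactly 20/20 are allocated at consent and k are lost at random (hypergeometric).**

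- k = 2: P(equal arms) = 20 × 20 / C(40,2) = 400/780 = 0.513, so P(difference ≥ 2) = 0.487.
- k = 4: P(equal) = 190² / 91,390 = 0.395, so P(≥ 2) = 0.605; P(≥ 4) = 2 × 4,845 / 91,390 = 0.106.
- k = 6: P(equal) = 1,140² / 3,838,380 = 0.339, so P(≥ 2) = 0.661; P(≥ 4) = (2 × 15,504 × 20 + 2 × 38,760) / 3,838,380 = 0.182.

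**3. Simulation of both timings at 40 starts.** 4,000 runs per setting, five independent binary factors at 50%, first five patients simple. The factor coding and the probability of taking the favoured arm are assumptions. Each cell gives the results for L = 5%, 10%, 15%.

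| Minimisation | Mean difference among operated patients | At consent | At booking |
|---|---|---|---|
| Deterministic | Arm size | 1.09, 1.47, 1.75 | 0.27, 0.27, 0.28 |
| Deterministic | Per factor level | 1.09, 1.28, 1.44 | 0.80, 0.79, 0.81 |
| Probability 0.8 | Arm size | 1.45, 1.74, 1.98 | 0.94, 0.95, 0.94 |
| Probability 0.8 | Per factor level | 1.53, 1.65, 1.73 | 1.37, 1.37, 1.36 |

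A separate run of 600 per setting agrees at 10% loss: 1.51 against 0.27 (deterministic) and 1.75 against 0.97 (probability 0.8).

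The percentages in step 2 need a comparator. The operated totals are even, so the arm difference is even and P(≥ 2) is at most half its mean. With deterministic minimisation at booking that is at most 0.28/2 = 0.14. With probability 0.8 a further 2,000-run simulation put it at 43% to 45%, so booking does not remove imbalance when minimisation has a random element.

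**4. Effect on precision.** For 34 operated patients split 19/15 rather than 17/17: (1/19 + 1/15) / (2/17) = 0.1193 / 0.1176 = 1.014, a 1.4% larger variance. Averaged over simulated trials, the inflation from unequal arms is 0.17% to 0.51% at consent against 0.04% to 0.05% at booking (deterministic), and 0.29% to 0.60% against 0.17% to 0.19% (probability 0.8).

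**5. Starts needed for 40 randomised at booking.** 40 / (1 − L) = 42.1, 44.4, 47.1, so 43, 45, 48.

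**6. Predictability.** Someone who knows only the running arm totals guesses the next arm correctly about 73% of the time from the 6th patient on (65% with probability 0.8), against 50% under simple randomisation. This holds under either timing.

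**The case against.** The case for leaving the timing alone is fair. Nothing in the protocol is contradicted. The number operated on is the same either way, the gain in variance averages under half a percentage point, and every loss rate is assumed. The eligibility rule asks for motivation to wear appliances for at least two years, which tends to limit loss. With a random element in minimisation, the gain per factor level shrinks to 0.16, 0.28 and 0.37 patients. Booking order would depend partly on when an unblinded orthodontist declares a patient ready, and a log records that decision without removing it. All of this stands. It lowers the priority but does not touch the sequence, which is plain in the text.

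Three stronger readings are tempting and are not supported.

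- A reader might infer that allocation at consent makes the randomisation invalid or biased. It does not: a comparison by allocated arm from consent remains valid, with missing outcomes whose handling may be left to the SAP.
- A reader might infer that early knowledge of the arm distorts the alignment phase. The protocol has one orthodontist following a fixed sequence, and no mechanism of bias can be shown from the text.
- A reader might infer from the group field on Annexure 2 that the readings cannot be masked. The field could be completed later or by someone else. What the text supports is only that no masking is planned and no reader is named.

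**Conclusion.** The point holds as an improvement of optional to moderate priority. Patients lost in alignment are randomised without receiving either technique and remain in the minimisation totals. Under random loss of 5% to 15%, moving allocation to booking would cut the mean arm-size difference among operated patients by about 0.8 to 1.5 (deterministic) or 0.5 to 1.0 (probability 0.8); the protocol does not say which applies. The consequence for precision is slight, and no gain in power or reduction in bias is claimed. The main benefit is a randomised set not eroded before the techniques diverge; the arm also stays unknown during the common phase.

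The masking of the Annexure 2 readings is a separate matter and lends no weight to this one.

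**What to change.** **Allocation.** Keep consent and baseline recording as now. Have the neutral staff assistant allocate once the full-size wire stage is reached and the surgery date is booked, strictly in the order of a dated booking log that the assistant keeps. Use factor values recorded at baseline, because alignment can change crowding, rotation and oral hygiene. The Baseline Data sheet shows no field for crowding or rotation, so state where these are recorded.

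Cost: protocol wording and a log. If 40 are to be randomised, 43, 45 or 48 patients must be started at 5%, 10% or 15% loss, at one centre within a 36-month schedule; if starts stay at 40, the number operated on is unchanged. The surgeon learns the arm later. Booking order must be protected because the next arm is partly predictable, as it already is at consent.

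**Separately, Annexure 2.** Replace the group field with the case number from the Baseline Data sheet. Keep the treatment-history items (6 to 8) off the reader's form; if they go to Annexure 3, bracket debonds need their own line, since that form counts button debonds. Have the readings taken by existing staff not involved in treatment; the blinded severity assessor is one candidate, if able to take clinical readings. This costs some staff time. Without such a reader, the form change should not be presented as masking.

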#### **2. Allocation concealment and implementation of the random allocation sequence:**

Blinding of the investigator is not possible so to reduce bias one of the staff assistant who was neutral towards treatment will be allocated the job of assigning patient in the two treatment groups. The first 5 patients will be allocated according to simple randomization and from 6th patient onwards minimization will be followed.

The prognostic factors or predictors will be used like severity of impaction, age, oral hygiene, presence of crowding, and rotation of canine. The severity of the canine impaction will be assessed by a single blinded assessor, from the pretreatment panoramic imaging film, using the criteria described by Ericson and Kurol.

### **Treatment Protocol:**

The orthodontic treatment will be done by single orthodontist who will follow a strict protocol as follows:

1. Initial orthodontic alignment will be aimed at creating space in the maxillary arch with fixed appliance therapy (0.022 slot) .The surgical procedure will be done after reaching a full size wire of 19X25 S.S with open coil spring to maintain space for the permanent canine. Anchorage preparation will also be done with the help of TPA.

#### 2. Surgical exposure and orthodontic traction.

The tooth will be sufficiently exposed to bond an orthodontic attachment (button). NiTi closed coil (0.018"S.S. wire) spring will be used to vertically extrude highly placed palatal canine impactions till the time it erupts sufficiently so as not to resorb the roots. After that traction force will be applied followed by ligature with e chain which will be hooked to the helix to get it in the line of arch once it has extruded sufficiently so as not to interfere with the roots. The duration of this phase (duration of traction) will be calculated as the time between the application of the traction device and the alignment of the impacted canine.

#### 3. Finishing: Orthodontic finishing of case to align the canine in the maxillary arch.

All surgical procedures will be carried out under local anesthesia by a single specialist (Oral and maxillofacial surgeon) having experience of practicing both surgical techniques: open and closed.

#### Open Surgical Exposure of Impacted canine:

- Surgically uncover the canine tooth and bone removal exposing the largest diameter of the ectopic canine crown. The edges need to be substantially trimmed back and dental follicle removed to prevent regrowth of the very thick palatal mucosa. For a deeply buried and palatally displaced tooth, the exposure will additionally need to be maintained using surgical pack.
- Coe-pack surgical dressing (GC America Inc, Alsip, IL) will be left in place.
- The patient will be reviewed 10 days later, the surgical pack will be removed and the bracket will be bonded and loading will be done by traction forces. Once the tooth has

erupted sufficiently for an orthodontic attachment to be positioned at its correct location to bring the tooth into line.

**Closed Surgical Exposure of Impacted canine:**

- Surgically, the palatal mucosal full thickness flap overlying the impacted canine will be raised and surgical bone removal exposing the largest diameter of the ectopic canine crown.
- An orthodontic attachment (button) with ligature wire and bracket with closed coil spring will be bonded to the palatal or buccal surface of the ectopic canine crown (whichever was the most accessible).

**Outcome Assessment:**

The following outcomes will be measured during and post orthodontic treatment:

**Primary Outcome Measures:**

1. Oral health based Quality of life of patients undergoing canine disimpaction will be accessed by questionnaire. (Annexure 1)
2. Measurement of width of attached gingiva. Measures which assess the periodontal outcome like crown length, gingival recession, bone will be assessed. (Annexure 2).

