**OBJECTIVES:**

1. To assess oral health related quality of life in patients undergoing canine disimpaction through Questionnaire.
2. To assess periodontal outcomes between the open and closed surgical techniques.
3. To assess whether there are differences in patient reported outcomes between the open and closed surgical techniques.

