### 3. METHODOLOGY:

**Study design:** A unicentric, randomized controlled clinical trial involving 2 parallel groups (Group 1 for open surgical technique and group 2 for closed surgical technique) where contralateral side fully erupted and normally positioned canine will be considered as control. The study will be conducted in Department of Orthodontics, Faculty of

Dentistry, Jamia Millia Islamia post ethical committee approval by institutional ethics committee.

Written informed consent will be taken from all the patients enrolling in the study.

Estimation of Sample Size: Assuming the mean difference of the primary outcome (measure of clinical attachment) as 0.5 mm with standard deviation as 0.61 mm between the open and closed exposure group (Reference : Periodontal health of palatally displaced canines treated with open or closed surgical technique: A multicenter, randomized controlled trial. American Journal of Orthodontics and Dentofacial Orthopedics August 2013 ; 176-84; Vol 144 ;Issue 2) with alpha (level of significance) <0.05 , Power=80% , 2 sided hypothesis, the total minimum sample size 40 will be required to detect the minimum significant difference of the primary outcome. The total sample size can be randomized in equal no. as 20 in each group (open and closed group). Twenty patients who meet the below mentioned criteria will be randomly allocated in each group. Participants for the trial will be identified from treatment waiting lists and new patient clinics.

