**4. EXPERIMENTAL SCHEDULE & OUTCOME FOR 3 YEARS:**

Time in Months	1-2m	2-12m	12-30m	30-36m
Training of Research Associate and enrollment of patients				

Implementation of project and treatment phase				
Data Analysis and compilation of results				

**5. SHADOW PRICING OF PROPOSED STUDY & MODALITIES:** This is a routine fixed orthodontic procedure in Dept. of Orthodontics, Faculty of Dentistry, Jamia Millia Islamia and materials related to this project will be provided by the institute.

**6. SCIENTIFIC IMPACT OF PROPOSED STUDY:** According to present literature, there is no evidence to support either the open or the closed technique for exposing palatally ectopic canines to be clinically superior in terms of dental health, aesthetics, economics and patient factors. There is a high need for randomized clinical trials on this subject, the current literature provides very weak evidence. Current evidence gaps need to be filled. Our study aims at providing evidence as to which technique should be used to expose palatally impacted canines, open or closed. It will take into consideration the primary outcomes like periodontal health of the disimpacted teeth as well as the secondary outcomes that is the patient reported outcomes including patient comfort and aesthetics. This study might provide some good evidence which could help the surgeon and orthodontist to decide the suitable approach for a particular case.

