**OUTCOME: Annexure 1;1**  
**Oral Health Impact Profile Questionnaire (OHIP-14)**  
**(Pre-treatment)**

S.no	Questions	Score (Tick any one)					
		Very Often	Fairly Often	Occasionally	Hardly ever	Never	Don't know
1.	Have you had trouble pronouncing any words because of problems with your teeth or mouth?						
2.	Have you felt that your sense of taste has worsened because of problems with your teeth or mouth?						
3.	Have you had painful aching in your mouth?						
4.	Have you found it uncomfortable to eat any foods because of problems with your teeth or mouth?						
5.	Have you been self-conscious because of your teeth or mouth?						
6.	Have you felt tense because of problems with your teeth or mouth?						
7.	Has been your diet been unsatisfactory because of problems with your teeth of mouth?						
8.	Have you had to interrupt meals because of problems with your teeth or mouth?						
9.	Have you found it difficult to relax because of problems with your teeth or mouth?						
10.	Have you been a bit embarrassed because of problems with your teeth or mouth?						
11.	Have you been a bit irritable with other people because of problems with your teeth or mouth?						
12.	Have you had difficulty doing your usual jobs because of problems with your teeth or mouth?						
13.	Have you felt that life in general was less satisfying because of problems with your teeth or mouth?						
14.	Have you been totally unable to function because of problems with your teeth or mouth?						

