**Annexure 1;3**

**Oral Health related Quality of life Questionnaire**  
**(24hrs after surgery)**

How much trouble you have with your teeth or mouth?

S.no	Questions	Score (Tick any one)				
		No trouble	A little trouble	Some trouble	Quite a lot trouble	Lots of trouble
1.	Eating/chewing foods you want					
2.	Opening your mouth wide					
3.	Sleeping					
4.	Talking to people so that they can understand you					
5.	Going about your everyday routine					
6.	Taking part in your social life					
7.	Taking part in sports					
8.	Swelling of your cheeks					
9.	Bruising					
10.	Bleeding					
11.	Nausea					
12.	Bad taste / bad breath					
13.	Food collecting in the hole after the teeth were pulled					
14.	Rate the worst pain you have felt in your teeth, mouth and face during past 24 hrs.	1	2	3	4	5

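### The outcome on which the trial is sized (clinical attachment) is not named among the primary outcomes, and 20 per arm gives about 71% power for it, not 80%

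*Protocol*

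**What the plan says.** Three parts of the protocol describe the primary outcome, and they differ.

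- **Section 3, Estimation of Sample Size.** The calculation begins "Assuming the mean difference of the primary outcome (measure of clinical attachment) as 0.5 mm", with SD 0.61 mm, a two-sided 5% level and 80% power. It concludes that "the total minimum sample size 40 will be required to detect the minimum significant difference of the primary outcome", split as 20 per group.
- **Primary Outcome Measures.** Entry 1 reads "Oral health based Quality of life of patients undergoing canine disimpaction will be accessed by questionnaire" and points to Annexure 1. Entry 2 reads "Measurement of width of attached gingiva. Measures which assess the periodontal outcome like crown length, gingival recession, bone will be assessed" and points to Annexure 2. Neither entry has a target difference or SD.
- **Section 6, Scientific Impact.** The study is said to consider "the primary outcomes like periodontal health of the disimpacted teeth as well as the secondary outcomes that is the patient reported outcomes".

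Objective 1 is "To assess oral health related quality of life in patients undergoing canine disimpaction through Questionnaire". Annexure 1 holds OHIP-14 before and after treatment, and a different questionnaire at 24 hours and at ten days after surgery. The protocol does not say which of these is the primary measure.

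**The concern.** A trial needs one agreed answer to the question of which result decides it, and the sample size should belong to that result. Here the only outcome with a target difference and SD is not named in the primary list, and the outcomes that are named have neither figure. The status of quality of life also changes from place to place: it is first among the objectives and first in the primary list, but section 6 puts patient-reported outcomes second.

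The candidates are clinical attachment, width of attached gingiva, several other periodontal measures, and two questionnaires at different times. With that many, the deciding result could be chosen after the data are seen. The protocol criticises earlier studies in this field for bias, so the point matters for its own purpose. A statistical analysis plan could add detail, but it cannot make conflicting protocol statements agree.

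The second matter is arithmetical. Even for clinical attachment, the stated inputs and the stated number of patients do not give the stated power.

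**Working it through.** **Comparison of the texts**

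| Place in protocol | Called primary | Target difference and SD |
|---|---|---|
| Section 3, sample size | Measure of clinical attachment | 0.5 mm, 0.61 mm |
| Primary Outcome Measures, entry 1 | Quality of life by questionnaire | None |
| Primary Outcome Measures, entry 2 | Width of attached gingiva, with crown length, recession, bone | None |
| Section 6 | Periodontal health; patient-reported outcomes secondary | None |

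The sized outcome and the listed outcomes share no named measure, and the second and fourth rows conflict over quality of life.

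**Reproducing the sample size**

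Inputs, all from section 3: difference 0.5 mm, SD 0.61 mm, two-sided alpha 0.05, power 0.80, equal groups.

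1. Standardised difference: d = 0.5 / 0.61 = 0.820.
2. Normal formula: n per arm = 2 × [(1.960 + 0.842) × 0.61 / 0.5]² = 23.4, so 24 per arm, 48 in total.
3. Two-sample t-test (noncentral t): 24.4, so 25 per arm, 50 in total. Power is 79.4% with 24 per arm and 81.0% with 25.

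Neither gives 40. A one-sided 5% t-test needs 19.1, so 20 per arm (81.6% power), which does match 40. The protocol specifies a two-sided hypothesis, so this is only a possible origin of the figure.

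**Power with 20 per arm, two-sided 5%**

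- Noncentrality: 0.820 × √(20/2) = 2.59.
- Normal approximation: Φ(2.59 − 1.96) = Φ(0.63) = 73.6%.
- t-test with 38 degrees of freedom: 71.4%.
- Difference detectable with 80% power: 0.909 SD, and 0.909 × 0.61 = 0.555 mm.

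**Sensitivity**

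| Evaluable per arm | Two-sided alpha | Power for 0.5 mm (t-test) |
|---|---|---|
| 20 | 0.05 | 71% |
| 18 (assumed) | 0.05 | 67% |
| 16 (assumed) | 0.05 | 61% |
| 20 | 0.025 | 60% |

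The section 3 calculation gives no dropout figure, so 18 and 16 are illustrations. The last row applies only if two primary outcomes are kept and alpha is split equally.

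**The case against.** **Attachment is not excluded from the list.** Entry 2 is open-ended: it gives examples of periodontal measures and refers to Annexure 2, where pocket depth, recession and probing bone level are recorded. A reader might infer that the protocol has dropped clinical attachment as a primary outcome. The text does not support that; attachment is unnamed, not ruled out. What remains is that an outcome called primary in one place has to be guessed at in the other. The protocol does not equate attached gingiva with clinical attachment, and it states no derivation of attachment from the recorded items.

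**Quality of life may not be a comparison between arms.** Objective 1 and entry 1 are worded without contrasting the techniques, and objective 3 covers that contrast separately. It would be tempting to say that every listed outcome can be detected only at 0.91 SD. That figure holds for comparisons between arms. If entry 1 means change from before to after treatment in all 40 patients, a paired t-test has 80% power at about 0.45 SD of the change.

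**What exactly was sized is not stated.** Section 3 gives no tooth, site or time point, and the contralateral canine is the control. One might read the 0.5 mm and 0.61 mm as the treated canine one month after debond. The protocol does not say so; they could equally refer to a difference from the control canine.

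**Some of this is the sponsor's choice or belongs in an analysis plan.** Whether quality of life stays primary is for the sponsor to decide, and not every listed outcome needs its own sample size. An alpha rule is commonly left to the analysis plan. These points limit the remedy, but they leave the contradiction and the power figure standing.

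**Conclusion.** The concern holds in two parts.

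1. The protocol contradicts itself on the primary outcome. The sample size rests on clinical attachment, the primary list does not name it, and section 6 disagrees with that list on quality of life. This follows from the wording alone and needs no assumption. It must be corrected, because it leaves open which result the trial will be judged on.
2. The stated 80% power is wrong for the stated inputs. It is about 71% by t-test (74% by normal approximation), and 80% corresponds to about 0.55 mm. This rests on a two-sided comparison of two independent groups with 0.61 mm as the within-group SD. The 71% is a ceiling, since it requires all 40 patients to be evaluable.

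A reader might go on to conclude that the trial must be enlarged. That does not follow: an honest statement of what 40 patients can detect is enough.

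**What to change.** 1. **Reconcile section 3, Primary Outcome Measures and section 6** so that one outcome is named as the basis for both the sample size and the conclusion. The simplest route is clinical attachment as the single primary comparison between arms, since it alone has a target difference and SD. State the tooth (the treated canine, or its difference from the contralateral control), the site and derivation, and the time point; Annexure 2 already uses one month after debond. Confirm that 0.5 mm and 0.61 mm refer to that measure.
2. **If the sponsor keeps quality of life as primary**, state which Annexure 1 instrument and time point is meant, whether it is a comparison between arms, and how alpha is handled. At 2.5% each, the power for 0.5 mm with 20 per arm is about 60%.
3. **Correct the power statement in section 3** to at most about 71% for 0.5 mm with 20 evaluable per arm, or 80% for about 0.55 mm, and say that dropout lowers it (about 67% if 18 per arm are evaluable).

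The cost is protocol wording and one corrected figure. No added patients are required; restoring 80% for 0.5 mm is optional and would take 25 per arm, 10 more in total before any dropout. The real downsides are that quality of life, which is objective 1, loses its primary label under the simplest route, and that the stated power becomes less favourable.
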